6.1 Inclusion and Exclusion Criteria

6.1.1 Inclusion Criteria

[figure not shown]
1. Seeking emergency (E) treatment including emergency room (ER) presentation
2. Paroxysmal AF diagnosed according to current ESC guidelines
3. Diagnosis of HFpEF according to ESC guidelines 2021 (clinical symptoms, EF>50%, objective evidence of functional abnormality: LV diastolic dysfunction, NT-proBNP (non acute setting): sinus rhythm: 125pg/ml or AF: 365pg/ml, vs. acute HF: >450 pg/ml if aged <55 years, >900 pg/ml if aged between 55 and 75 years and >1800 pg/ml if >75ys.
4. Age between 18 and 80 years
5. Left atrial size, LA < 55mm
6. Left ventricular ejection fraction, EF >50%
7. Patients able to provide informed consent and willing to comply with all pre-, post- and follow-up requirements as per study protocol

6.1.2 Exclusion Criteria

1. Currently participating in an interventional (drug, device, biologic, etc.) clinical trial
2. Any disease that limits life expectancy to less than one year
3. Contraindications for PVI
4. Contraindication for AAD therapy
5. Active systemic infection
6. Thrombocytosis, thrombocytopenia
7. Known pre-existing hemi-diaphragmatic paralysis
8. Any untreated or uncontrolled hyperthyroidism or hypothyroidism
9. Reduced immune function or otherwise at high risk for infection per physician discretion
10. Active malignancy or history of chemotherapy or radiation treatment
11. Prior left atrial ablation or surgical procedure (including left atrial appendage closures)
12. Any cardiac surgery, myocardial infarction, PCI/PTCA or coronary artery stenting which occurred within the 3 months before the eligibility assessment

13. Instable angina pectoris
14. Primary pulmonary hypertension
15. Any condition contraindicating chronic anticoagulation
16. Any cerebral ischemic event (strokes or TIAs) which occurred within the 3 months before the consent date
17. Presence of any cardiac prosthetic valves
18. Left atrial diameter > 55 mm (anteroposterior) by TTE
19. Presence of any pulmonary vein stents
20. Presence of any pre-existing pulmonary vein stenosis (identified by CT or MRI and defined as at least 70% reduction of the PV diameter)
21. Endocarditis, pericarditis or pericardial effusion
22. Pregnant or breastfeeding women or women of childbearing potential not on adequate birth control.
23. Substance abuse
24. Unwilling to follow the study protocol and to attend follow-up visits

6.2 Study course

6.2.1 Visit 1, Pre-procedural, Day -2 to 0

Following emergency hospital admission diagnostic work up including physical examination, 12 lead ECG, emergency blood examination (NT-proBNP) and chest X-ray initial cardiac ultrasound. Initiation and optimization of emergency therapy including iv diuretics if required. Routine diagnostic work up during hospital stay including daily clinical evaluation, weight loss determination, complete cardiac ultrasound, 12 lead ECG, telemetry, routine blood examination (30 ml) for blood cell count, INR, creatinine, ALAT, ASAT, electrolytes, TSH, NT-proBNP according to clinical needs.

Randomization (1:1) will be performed by the E-TEAM after all the patients' questions were clarified and the ICF was signed. All patients randomized to Group 1 will proceed to preparation of Visit 2, pulmonary vein isolation. The patients randomized in Group 2 will receive best medical treatment and if rhythm control was attempted TEE guided cardioversion and AAD according to the patients clinical needs as well as all information regarding the medical treatment.

In order to exclude intracardiac thrombi, a transesophageal echocardiogram (TEE) will be performed in patients randomized to Group 1 and considered at risk for thrombus formation and stratified to rhythm control (Group 2, before cardioversion). In case of TEE proven LAA thrombus the scheduled AF ablation or cardioversion can be postponed.

6.2.2 Visit 2, Pulmonary Vein Isolation, FARAPULSE-Ablation

The FARAPULSE ablation procedure will be performed during deep sedation using midazolam, fentanyl and a continuous infusion of propofol. Vital parameters will be monitored. For catheter access, two 8F sheaths will be inserted into the femoral veins guided by ultrasound. One multipolar diagnostic catheter will sequentially be placed in the coronary sinus and right ventricle to pace for in case of need. Single transseptal puncture and insertion of one 8.5 F transseptal sheath will be followed by PV angiographies. Using the FARAPULSE catheter, pulmonary vein (PV) electrograms will be recorded. Unfractionated heparin will be administered to maintain an activated clotting time between 300 and 400s. The FARAPULSE catheter will be advanced via a steerable sheath to the LA and sequential PV isolation will be performed for each individual PV following the recommended dosing strategy (1+7 applications: 4 basket, 4 flower configuration). In case of incessant AF or atrial flutter, additional ablation including right atrial isthmus ablation is allowed. At the end of the ablation procedure, the patients will undergo transthoracic echocardiography (TTE) on the table to exclude acute pericardial effusion.

6.2.3 Visit 3, Hospital Discharge

Until discharge, all patients will be monitored using telemetry and all patients in Group 1 will undergo a repeat TTE to exclude pericardial effusion and a daily 12 lead electrocardiography (ECG) to document the heart rhythm. A blood sample (20 ml) will be routinely collected to exclude bleeding (blood cell count) or renal function deterioration (creatinine and electrolytes). Therapeutic anticoagulation preferentially using a novel oral anticoagulant (NOAC) over Vitamin K antagonist will be initiated or resumed the evening after the procedure and maintained for at least 8 weeks after ablation. Continued anticoagulation will be performed if necessary, according to the individual CHA2DS2-Vasc-Score. In both groups early cardioversions in case of very early recurrence during the index hospital stay are allowed. AAD treatment in Group 1 should be avoided and should be stopped after 3 months, in Group 2 AAD treatment is allowed if rhythm control was selected according to the patients clinical profile. Total nights spent in hospital will be counted.

6.2.4 Visit 4, 3 Months Follow-Up after PVI/Randomization (\pm 7 Days)

An outpatient visit including the collection of a brief history (complications, medication), physical examination, 12 lead ECG, TTE and 72h-Holter-ECG will be performed at 3 Months \pm 7 Days post procedure (Group 1) or post randomization (Group 2). All antiarrhythmic drugs (AAD) except beta-blockers prescribed for other medical conditions (i.e. arterial hypertension) have to be stopped for all patients in Group 1. If necessary, all medication including AAD for the patients in Group 2 should be adjusted.

6.2.5 Visit 5, 6 Months Follow-Up after PVI/Randomization (\pm 14 Days)

An outpatient visit including the collection of a brief history (complications, medication), physical examination, 12 lead ECG, TTE and 72h-Holter-ECG will be performed at 6 Months \pm 14 Days post procedure (Group 1) or post randomization (Group 2).

6.2.6 Visit 6, 12 Months Follow-Up after PVI/Randomization (\pm 14 Days)

An outpatient visit including the collection of a brief history (complications, medication), physical examination, 12 lead ECG, TTE and 72h-Holter-ECG will be performed at 12 Months \pm 7 Days post procedure (Group 1) or post randomization (Group 2).

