
4. Methods

Symptomatic paroxysmal AF patients diagnosed with HFpEF seeking emergency treatment that meet all inclusion and none of the exclusion criteria will be randomized according to E-TEAM in two groups (1:1 randomization) as follows:

Group 1: early catheter ablation within 7 days post AF-related emergency treatment using the FARAPULSE electroporation technology (n = 100)

OR

Group 2: best medical AF treatment including rhythm and rate control (n=100)

All patients will receive (direct) oral anticoagulation and heart failure treatment according to their CHA₂DS₂-VASC Score and current ESC guidelines ^{1 2}.

5. Ablation

The FARAPULSE AF ablation system represents a unique single shot ablation technology associated with a high rate of acute and durable PV isolation ¹⁴. In principle, electroporation delivers a cardiac selective ablation, thus sparing non-cardiac tissue. The endpoint of the catheter ablation procedure is defined to PVI. Therefore, this technology offers a unique beneficial profile combining a high procedural efficacy and safety.

6. Endpoints

The **primary endpoint** is a composite of cardiovascular hospitalization (worsening heart failure, acute coronary syndrome, AF/AT recurrence, cardioversions, re-ablations), death, systemic embolism, stroke (ischemic, hemorrhagic) and emergency (E) treatment for cardiovascular reasons.

Secondary endpoints are defined to safety parameters such peri-procedural complications (major bleeding requiring intervention, phrenic nerve palsy, pericardial tamponade, thromboembolic events, atrio-esophageal fistula, death) or discontinuation of AAD due to side effects and documented recurrence of AF or any atrial tachyarrhythmia lasting longer than 30 seconds between day 90 and 365 after the index procedure as well as number of nights spent in the hospital per year.

Study Design

The proposed pilot study is a prospective, randomized, single-center feasibility study, enrolling 200 patients with symptomatic paroxysmal AF. Per protocol, 100 patients will undergo a FARAPULSE electroporation PVI and 100 patients will receive standard AF medical treatment.

Prior enrollment, all patients will be informed on the risk and benefits of the PVI procedure as well as the medical treatment. In addition, particular information on the rationale of the study, including a detailed risk/benefit analysis, will be provided to all patients.

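### Follow-up visits run from PVI in Group 1 but from randomization in Group 2, and the day 90–365 recurrence window is tied to an index procedure that Group 2 does not have

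*Protocol*

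**What the plan says.** Randomization takes place at the visit headed "6.2.1 Visit 1, Pre-procedural, Day -2 to 0". PVI comes afterwards: "All patients randomized to Group 1 will proceed to preparation of Visit 2, pulmonary vein isolation". The Methods section plans ablation within 7 days, counted from the emergency treatment. Section 6.2.1 allows exceptions and sets no upper limit: "In case of TEE proven LAA thrombus the scheduled AF ablation or cardioversion can be postponed".

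Sections 6.2.4, 6.2.5 and 6.2.6 each schedule the outpatient visit and its 72-hour Holter "post procedure (Group 1) or post randomization (Group 2"). Their headings repeat the pairing of PVI with randomization. Tolerances are ±7 days at 3 months and ±14 days at 6 months. At 12 months the heading gives ±14 and the text ±7.

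The Endpoints section defines recurrence as AF or another atrial tachyarrhythmia of more than 30 seconds "between day 90 and 365 after the index procedure". It also lists "number of nights spent in the hospital per year" as a secondary endpoint and names no start for that year. Section 6.2.3 adds only "Total nights spent in hospital will be counted". The Study Design section gives a follow-up of 12 months without an origin. No section names an origin for the primary endpoint.

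**The concern.** A randomized comparison needs one time zero for both groups, and it should be randomization. Here the protocol is not merely silent. It sets one visit clock per group, three times over, and anchors a comparative endpoint to an event that only one group is assigned.

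Three things are at stake:

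- The recurrence comparison cannot be carried out as defined, because one of the two groups has no window.
- Group 1 patients who never receive PVI belong in a comparison by assigned group, yet the schedule gives them no 3-, 6- or 12-month date.
- Group 1 patients with postponed PVI are examined later after randomization than Group 2, by the full length of the delay.

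**Working it through.** The protocol states no figure to reproduce. The check is a reading of the sections against each other, plus calendar arithmetic.

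**Does Group 2 have an index procedure?** Group 2 is assigned medical treatment. Section 6.3 uses the term for the ablation that may be followed by re-ablation and, at day 90, by the drug stop in the ablation group. The Study Design section advises PVI for Group 2 patients who deteriorate, but it does not call this the index procedure. It would reach only some patients, and only after an outcome-related event. It cannot serve as Day 0.

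**How long is the gap *d* from randomization to PVI?**

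- Routine: 0–2 days, reading Day 0 in the Visit 1 heading as the day of PVI.
- Planned maximum: 7 days. The 7 days run from emergency treatment, which precedes randomization, so *d* ≤ 7.
- Postponed for thrombus: no limit stated. I assume 28 and 56 days for illustration.
- PVI cancelled: *d* does not exist.

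**Where do Group 1's dates fall, counted from randomization?** The recurrence window is 90 + *d* to 365 + *d*, and the nominal 12-month visit is at 365 + *d*.

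| *d* (days) | Recurrence window | 12-month visit | *d*/365 |
|---|---|---|---|
| 2 | 92–367 | 367 | 0.5% |
| 7 | 97–372 | 372 | 1.9% |
| 28 (assumed) | 118–393 | 393 | 7.7% |
| 56 (assumed) | 146–421 | 421 | 15.3% |
| PVI cancelled | undefined | undefined | – |

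Group 2's 12-month visit is at day 365, and its recurrence window is undefined as written. It would be 90–365 if randomization were substituted.

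**How does this compare with the tolerances?** A gap of 0–7 days does not exceed the tightest tolerance of ±7 days. A 28-day delay exceeds the widest, ±14.

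**Could an analysis plan repair this alone?** It could set randomization as the origin for analysis, but it cannot move a visit. With a 28-day delay and the wider tolerance, the 12-month Holter may fall no earlier than day 393 − 14 = 379, which is already outside a window that ends at day 365 from randomization.

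**The case against.** The strongest reply is that a visit schedule is not an endpoint clock. Sections 6.2.4 to 6.2.6 arrange outpatient visits, no section counts the primary endpoint from PVI, and the analysis origin is commonly left to the analysis plan, which is not at hand. This stands for the primary endpoint. It does not stand for recurrence, whose window the protocol itself ties to the procedure.

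A second reply is that the Group 2 window has an evident meaning, since the visit headings pair PVI with randomization. That is the likely intent. But it leaves the groups on different clocks and gives no date to a Group 1 patient without PVI.

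A third reply is that the procedure clock serves a purpose, because Visit 4 carries the Group 1 drug stop. That is true, and the remedy has to preserve it.

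A reader might go further and infer that the clock biases the primary endpoint in favour of ablation, by leaving early Group 1 events before time zero. The protocol does not say so. Even if Group 1 were counted from PVI, a constant hazard gives no bias. Assuming a hazard 3–5 times higher in the first 30 days and a 12-month risk of 30–50%, the shift is 0.2–0.6 percentage points for a 2-day gap and 0.8–2.0 for 7 days. With 100 per group, the standard error of the risk difference is √(2 × 0.3 × 0.7/100) = 6.5 points to √(2 × 0.5 × 0.5/100) = 7.1 points. The routine shift is under a tenth of that. The raised hazard has no source in the protocol. It also fits poorly with patients still in the index stay, who cannot be newly admitted, so even the sign is uncertain.

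A reader might likewise infer that up to 2 waiting nights per patient drop out of Group 1's hospital nights. Section 6.2.3 counts total nights at discharge, which most naturally covers the whole index stay, and nothing excludes nights before PVI.

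**Conclusion.** The point holds for the visit schedule and the recurrence endpoint, and it should be corrected. By the protocol's own wording, the recurrence comparison has no window in Group 2, and Group 1 patients with cancelled PVI have no visit dates. Neither conclusion needs an assumption. For postponed PVI, visits and window shift day for day with the delay. The 28- and 56-day figures are illustrations, and the protocol gives no basis for how many patients this affects.

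The routine misalignment, 0–2 days and at most 7, is unimportant in itself. No bias in the primary endpoint or in hospital nights is shown. For those two the finding is only that the origin is unstated, and it is sensible to name it while the other text is being amended.

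**What to change.** Amend sections 6.2.1, 6.2.4 to 6.2.6 and the Endpoints section as follows:

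- Define randomization as Day 0 in both groups for the 3-, 6- and 12-month visits and for the day 90–365 recurrence window.
- State the same origin for the primary endpoint and for nights per year.
- Analyse by assigned group, and say explicitly that Group 1 patients with postponed or cancelled PVI keep the same visits and windows.
- Keep the procedure clock only for peri-procedural complications and for the Group 1 drug stop at 90 days.

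The cost is a wording amendment. Routine Group 1 visits move 0–2 days, at most 7, which is within tolerance.

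There are two downsides. Events before PVI will count against the ablation strategy, which is the fair comparison for a strategy assigned at randomization. And where PVI is postponed, the drug stop no longer coincides with Visit 4: with a 28-day delay, day 90 from randomization is only day 90 − 28 = 62 after PVI. Those few patients may need one extra contact, and their recurrence window then opens earlier after ablation than it does now.

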6.3 Repeat ablation

No blanking period will be utilized in this study. During the first 90 days after the index procedure any arrhythmia recurrence shall be treated conservatively, e.g. by antiarrhythmic medication and/or ECV. Of note, re-ablation is strongly discouraged within the first 3 months. At day 90 however, all AAD drugs should be stopped in the ablation group and all re-ablation afterwards will meet the primary endpoint. In case of re-ablation the patient has reached the primary endpoint. The Follow-Up visits should be continued as per protocol.

7. Participant withdrawal or termination of participation

Prior to study entry, all participants will be informed that they are free to withdraw from the study at any time and for any reason without prejudice to their future medical care by a physician or the institution. Participants are free to withdraw from participation in the study at any time upon request. The withdrawal will cause no penalty or loss of benefits, to which the patients may otherwise be entitled. The investigator may ask and document the patients' motivation.

An investigator may also terminate a patients' participation in the study if:

- Withdrawal is in the subjects' best interest.
- Subject withdraws consent.
- Subject is lost to follow up.

8. Statistical Analysis

No interim-analysis will be performed.

The following events will trigger a premature study termination:

- Occurrence of serious adverse events in more than 10% of the study population associated with the ablation procedure. Of note, re-hospitalization for cardiovascular reasons meets the primary study endpoint.
- Occurrence of any unexpected, currently unknown complication or risk (Change of Risk-Benefit Ratio).

Occurrence of >10% major procedural complications defined as cardiac tamponade, stroke/TIA, air embolism, major bleeding the study has to be stopped. Of note re-hospitalization for cardiovascular reasons meets the primary endpoint.”

9. Adverse Events

All adverse events (AEs) experienced by participants during the study, beginning with the first study related procedure and continuing through the end of study, will be recorded on case report forms (CRFs). Occurrences of atrial fibrillation and atrial flutter will be recorded and reported on as part of the efficacy assessment, and are not considered adverse events.

Serious adverse events (SAEs) are events that place the participants health in jeopardy and that occur despite following all labeling precautions and instructions for use and where all attempts at correction by medical intervention do not resolve the event. All SAEs must be reported to the Ethics Committee (EC) within 48 hours of the investigator becoming aware of the SAE. Re-hospitalization for cardiovascular reasons is part of the primary endpoint and therefore does not qualify as an SAE.

An unanticipated adverse device effect (UADE) is defined as any SAE on health or safety, or any life-threatening problem or death caused by, or associated with, the device, if that effect, problem, or death was not previously identified in nature, severity, or degree of incidence in the investigational plan or application. An UADE is also defined as any other unanticipated serious problem associated with a device that relates to the rights, safety, or welfare of participants.

Should an UADE occur, the investigator is required to notify the EC as soon as possible, but in no event later than 10 working days after the investigator first learns of the event. An immediate evaluation of any UADE will be conducted. If there is significant new information that could affect the risk/benefit analysis as given in Section 7.1 of this protocol, the ECs will be informed and if appropriate, actions such as study hold, patient re-consent or study termination will be taken.

All participant deaths must be immediately reported to the EC (24 h upon investigators knowledge). When possible and permitted by family members, an autopsy shall be performed. The death certificate, coroner's report, and laboratory and autopsy reports, if available, should be provided to the EC.

10. Documentation

All patient data will be documented in CRFs. Personal data such as name, address, contact data etc. are excluded from the documentation in the eCRF. Names of all patients will be pseudomized and underlie national data protection laws. The principal investigator will conserve the patient identification list, the signed informed consent forms and the original data including the patient chart for 15 years.

11. Study organization

Principle Investigators: [name]. med. [name]
MVZ CCB Frankfurt und Main Taunus GbR
Am Agaplesion Markus Krankenhaus
[name]
[contact]
Fax: [name]
E-Mail: [contact]

Priv. Doz. Dr. med. [name]

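### The SAE definition requires compliance with the instructions and failure of treatment, so a serious ablation complication that is treated successfully gets no 48-hour ethics committee report and is left out of the SAE stopping trigger

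*Protocol*

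**What the plan says.** Section 9 (Adverse Events) contains the only SAE definition in the protocol. It has three parts, all of which must hold: the event places the participant's health in jeopardy; it is one of those "that occur despite following all labeling precautions and instructions for use"; and it is one "where all attempts at correction by medical intervention do not resolve the event".

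Two safeguards use the term:

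- Section 9, reporting: "All SAEs must be reported to the Ethics Committee (EC) within 48 hours" of the investigator becoming aware.
- Section 8, first stopping trigger: "Occurrence of serious adverse events in more than 10% of the study population associated with the ablation procedure".

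Section 9 adds an exemption: "Re-hospitalization for cardiovascular reasons is part of the primary endpoint and therefore does not qualify as an SAE". Section 8 attaches a similar remark to the trigger: "Of note, re-hospitalization for cardiovascular reasons meets the primary study endpoint".

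Other provisions do not depend on this definition, or only in part. All adverse events are recorded on CRFs (Section 9). Deaths go to the EC within 24 hours. The unanticipated adverse device effect (UADE) route applies "if that effect, problem, or death was not previously identified in nature, severity, or degree of incidence", with notice as soon as possible and "in no event later than 10 working days after the investigator first learns of the event". Section 8 also stops the study for an unexpected, currently unknown complication or risk, and for more than 10% major procedural complications (tamponade, stroke/TIA, air embolism, major bleeding).

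**The concern.** Seriousness should describe the event. Here it depends on whether the operator followed the instructions and on whether treatment worked. A complication that needed urgent intervention can lose SAE status because the intervention succeeded, and one that follows a departure from the instructions never has it.

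This is an open trial with an invasive arm, and Section 8 plans no interim analysis. Event-by-event reporting and the stopping triggers therefore carry much of the safety oversight during the trial. If the definition is followed as written, the EC does not hear promptly of known, non-fatal serious complications that resolved, and the SAE rate reported at the end understates what ablated patients went through.

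**Working it through.** **1. Which provision catches which event.** No figure in the protocol can be reproduced here, so the check is a comparison of provisions. Take a known, non-fatal, serious ablation complication that treatment resolves.

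| Provision | Does it catch the event? |
|---|---|
| 48-hour EC report (Section 9) | No: it covers SAEs only, and the non-resolution condition fails |
| SAE trigger, >10% (Section 8) | No, for the same reason |
| CRF recording (Section 9) | Yes, but without prompt EC notice |
| UADE route (Section 9) | Only if unanticipated in nature, severity or incidence; up to 10 working days |
| 24-hour death report (Section 9) | No: non-fatal |
| Unknown-risk trigger (Section 8) | No: a known complication |
| Four-event >10% rule (Section 8) | Yes for tamponade, stroke/TIA, air embolism and major bleeding; otherwise no. It creates no EC report |

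An event that follows a departure from the instructions gives the same pattern, because the compliance condition then fails.

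Resolved events outside both 10% rules include phrenic nerve palsy and atrio-esophageal fistula (both safety endpoints in Section 6), and systemic infection and pulmonary vein stenosis (both listed in the Risk-Benefit-Analysis).

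**2. Size of the trigger.** The trigger refers to the study population, which could mean all 200 patients or the 100 ablated.

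- More than 10% of 100: at least 11 patients.
- More than 10% of 200: at least 21 patients.

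**3. Would it fire at the protocol's own rates?** Upper ends of the non-fatal rates in the Risk-Benefit-Analysis, per 100 ablated: vascular access 3, tamponade 1, systemic infection 1, thrombo-embolic 1, pulmonary vein stenosis 0.5, fistula 1.

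3 + 1 + 1 + 1 + 0.5 + 1 = 7.5 per 100.

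Assume every such event is serious, counts, and occurs in a separate patient. The number of patients affected is then binomial (n = 100, p = 0.075):

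- P(at least 11) = 0.13.
- P(at least 21) = about 0.00001.

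So at these rates the trigger rarely fires even under a corrected definition. The figure of 7.5 is not a strict upper bound, since no rate is given for phrenic nerve palsy. In the other direction, some listed events, such as hematoma, need not be serious, and events can overlap in one patient.

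**4. If the true rate were much higher.** The rates and resolved shares here are assumptions. For 100 ablated patients and a limit of 11, the chance of reaching the SAE trigger is P(X ≥ 11) with X binomial (100, rate × (1 − resolved share)):

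| True serious rate | None resolve | 25% | 50% | 75% |
|---|---|---|---|---|
| 15% | 0.90 | 0.58 | 0.13 | 0.001 |
| 20% | 0.99 | 0.90 | 0.42 | 0.01 |

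This describes the SAE trigger alone. The four-event rule runs beside it.

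**5. EC reports not made.** Missing reports per 100 ablated = 7.5 × share serious × share resolved. The shares are assumptions (50–100% serious, 30–80% of those resolved).

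- Lowest: 7.5 × 0.5 × 0.3 = 1.1
- Highest: 7.5 × 1 × 0.8 = 6.0

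The highest figure requires every listed event to be serious, including access-site hematoma.

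**The case against.** The strongest reply is that other provisions cover the serious cases. Tamponade, stroke/TIA, air embolism and major bleeding count in their own 10% rule whatever their outcome. Deaths and unanticipated device effects have separate routes, and new information that bears on the risk-benefit balance must go to the EC. This stands, and it limits the point to known, non-fatal complications. It does not restore the 48-hour report for any of them, nor bring the other resolved complications into a 10% rule.

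Four stronger readings are tempting, and the protocol does not support them.

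- **The nominal 10% limit becomes a much higher one.** A reader might divide 10% by the unresolved share. That isolates one trigger from the four-event rule and rests on shares the protocol does not give. At the protocol's own rates neither version of the trigger is likely to fire.
- **Section 9 contradicts the safety endpoint.** Section 6 counts major bleeding requiring intervention, and such a bleed is no SAE once it is controlled. But nothing says that every endpoint event must be an SAE. This is a gap between two classes of event and not a contradiction.
- **The 48-hour clock cannot start until all treatment has failed.** Section 9 does not say when resolution is judged. This is one possible reading and not a stated rule.
- **The readmission exemption removes procedural complications.** It exempts the readmission and is silent on a complication behind it. Exempting pure endpoint events is a deliberate choice that the sponsor may keep.

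**Conclusion.** The point holds in limited form. As written, Section 9 makes SAE status depend on compliance and on failed treatment. Known, non-fatal serious ablation complications that resolve, or that follow a departure from the instructions, therefore fall outside the 48-hour EC report and the SAE-based trigger. This follows from the wording and needs no assumption.

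The practical loss is mainly prompt EC notice and a meaningful SAE rate, with perhaps 1 to 6 unreported events per 100 ablated under the assumed shares. The effect on stopping is secondary. At the protocol's upper rates the chance of reaching 11 of 100 is about 0.13 even if everything counts, and dilution matters only if true rates are well above those stated. The primary endpoint is not affected. The change is still needed, because this definition governs safety reporting for the invasive arm and is easily put right.

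**What to change.** In Section 9:

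- Delete the conditions "that occur despite following all labeling precautions and instructions for use" and "where all attempts at correction by medical intervention do not resolve the event".
- Define seriousness by the event itself, whatever its outcome or the user's compliance: it leads to death, is life-threatening, requires or prolongs hospitalization, causes lasting impairment, or needs intervention to prevent one of these.
- Keep the exemption for cardiovascular re-hospitalizations that are only primary-endpoint events. Without it, the hospitalization criterion would make every such readmission an SAE, against the sponsor's stated choice. Add that a procedure- or device-related complication that causes a readmission remains an SAE.

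In Section 8, state whether the 10% of the SAE trigger refers to the ablated patients or to everyone enrolled, and align its remark on re-hospitalization with the revised Section 9.

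The cost is protocol wording and a few more EC reports: about 1 to 6 per 100 ablated under the assumptions above, plus any other event in either group that meets the new criteria, which the protocol gives no basis to count. The reported SAE rate will look less favourable, and the SAE trigger can be reached sooner. No patients or procedures are added.
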